11.2.3. Secondary Analyses

While our primary analysis focus on time to first event, we will collect data on all events occurring during follow-up and conduct recurrent event analyses.

In secondary analyses, we also will compare the effect of sham NOXT vs. NOXT on secondary endpoints including patient-reported outcomes; exercise capacity; disease-specific causes of re-hospitalization and death; and cardiovascular events.

Secondary analyses are considered exploratory and will be tested at significance level of 0.05 without adjusting for multiple comparison. Secondary endpoints will be analyzed according to type of scale. Time-to-event endpoints will be analyzed analogously to the primary endpoint. To assess the treatment effect on time to first HF-related hospitalization and CV mortality, mortality from other causes will be treated as a competing risk. Cause-specific cumulative incidence functions, instead of the standard Kaplan-Meier method, will be used to describe the probability of event occurring over time. Treatment effect will be quantified by cause-specific hazard ratios, obtained from Cox regression models, and care will be taken in interpreting the resulting HRs as among those who did not yet experience the event of interest or a competing event. Categorical variables will be analyzed using Fisher's exact tests or chi-square tests. Continuous endpoints will be compared using Wilcoxon rank-sum tests. Generalized linear models will be fit to assess the treatment effect on various endpoints adjusting for covariates for continuous, dichotomous or count data. Cox proportional hazard models will be used for time-to-event endpoints.

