3.1.2. Secondary Endpoints

Morbidity and Mortality

- All-cause mortality, CV interventions, or hospitalization for worsening HF (recurrent event analyses)
- CV death, life-saving CV interventions, or hospitalization for worsening HF (time-to-first event and recurrent event analysis)
- All-cause mortality or life-saving CV interventions (time-to-first event analysis)
- CV mortality or life-saving CV interventions (time-to-first event analysis)
- All-cause mortality (time-to-event analysis)
- CV Mortality (time-to-event analysis)
- Rate of hospitalization for worsening HF (recurrent event analysis)

Quality of Life and Symptoms

- Change in HF disease-specific quality of life, assessed by Kansas City Cardiomyopathy Questionnaire (KCCQ)
- Change in generic-quality of life, assessed by the EQ-5D
- Change in depressive symptoms assessed by the PHQ-8
- Change in sleep symptoms and sleep related daytime impairment (including fatigue), assessed by the PROMIS Sleep Disturbance and Sleep Related Impairment Questionnaires

Functional Status

- Change in NYHA Functional Class Ranking

Secondary morbidity and mortality endpoints will be measured over the full duration of study follow up. Quality of life, symptom, and functional status endpoints will be measured at baseline and at 6 and 12 months follow up.

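### Section 11.2.3 names no order-respecting, baseline-adjusted method for the ordinal NYHA endpoint, and lists exercise capacity, which the trial does not measure

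*Combined protocol and SAP*

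**What the plan says.** Section 3.1.2 has one item under Functional Status: "Change in NYHA Functional Class Ranking". Its timing is given as: "Quality of life, symptom, and functional status endpoints will be measured at baseline and at 6 and 12 months follow up".

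Section 11.2.3 gives no method endpoint by endpoint. It states a general rule, "Secondary endpoints will be analyzed according to type of scale", and then applies it:

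- categorical variables, followed by continuous endpoints: Fisher's "exact tests or chi-square tests. Continuous endpoints will be compared using Wilcoxon rank-sum tests";
- adjusted analyses: "Generalized linear models will be fit to assess the treatment effect on various endpoints adjusting for covariates for continuous, dichotomous or count data".

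NYHA class is not mentioned in 11.2.3, ordinal data are not mentioned, and no covariate is named. The section does list, among the secondary endpoints to be compared, "patient-reported outcomes; exercise capacity; disease-specific causes of" re-hospitalization and death. It also declares all secondary analyses exploratory, at the 0.05 level without multiplicity adjustment.

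**The concern.** NYHA class is an ordered scale with four levels. A chi-square or Fisher test on it, or on its change, treats the levels as unrelated labels. A shift in one direction is then spread over several degrees of freedom, and the test statistic does not say which arm did better. A real improvement in function would be more likely to be missed.

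Baseline matters too. Under section 5.2.2 patients enter in class II, III or IV. A class IV patient cannot get worse on the scale, and a class II patient can improve by only one class, so the possible change depends on entry class. The plan states no adjustment for it.

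The section also names a functional measure that the trial does not collect and leaves out the one that it does. More than one test can be defended for NYHA change, so the choice could be made after the data are seen.

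**Working it through.** **1. The plan's own secondary power figures.** Section 11.3 states 80% power with 429 per arm, two-sided 5%. For a binary endpoint with a pooled Z-test, power = Φ{[d√n − 1.96√(2p̄(1−p̄))] / √(p₀(1−p₀)+p₁(1−p₁))}, where d = p₀ − p₁ and p̄ is their mean.

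- Control risk 20%, 35% reduction (p₁ = 0.13): 79.0%.
- Control risk 40%, 23% reduction (p₁ = 0.308): 80.6%.
- Control risk 60%, 16% reduction (p₁ = 0.504): 80.8%.

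For a difference of 0.2 SD, power = Φ(0.2√(n/2) − 1.96). This is 83.4% at n = 429, and 79.4% at n = 386, which is 429 less the planned 10% drop-out. The stated figures hold. None of them covers an ordinal endpoint.

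**2. Where NYHA change falls in 11.2.3.**

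| Reading of NYHA change | Method that follows | Uses order? | Named covariates |
|---|---|---|---|
| Categorical | Fisher or chi-square | No | None |
| Numeric score | Wilcoxon rank-sum | Yes | None |
| Adjusted model | Generalized linear model for continuous, dichotomous or count data | Only if recoded as a number or a two-level variable | None named |

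The first reading is the most natural for a class variable, but the text does not settle it.

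**3. What the unordered reading would cost.** The documents give no NYHA distribution and no expected effect, so the inputs are assumptions: three control distributions, and a proportional shift with a common odds ratio (OR) of 1.3, 1.4 or 1.5. The treated distribution comes from multiplying each cumulative odds by the OR. Chi-square power uses the noncentral chi-square with k − 1 degrees of freedom and noncentrality n Σ[(p₀−p̄)²/p̄ + (p₁−p̄)²/p̄]. The comparator is a tie-corrected Wilcoxon test, 6,000 simulated trials per setting. It corresponds to the score test of a proportional-odds model without covariates.

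Worked case, improved/same/worse, OR 1.5, n = 429:

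- Control is 0.25/0.60/0.15, so the cumulative odds are 0.25/0.75 = 0.333 and 0.85/0.15 = 5.667.
- Times 1.5: 0.5 and 8.5. The cumulative probabilities become 0.333 and 0.895, and the treated arm 0.333/0.561/0.105.
- The three terms of the sum are 0.0119, 0.0013 and 0.0078, in total 0.0210. Noncentrality = 429 × 0.02103 = 9.02.
- With 2 degrees of freedom and critical value 5.99, power is 77%. The rank test gives 85%.

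All settings, power in %, unordered chi-square / rank test:

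| Assumed control distribution | n per arm | OR 1.3 | OR 1.4 | OR 1.5 |
|---|---|---|---|---|
| Improved/same/worse, 25/60/15 | 429 | 40 / 49 | 60 / 70 | 77 / 85 |
| Five change levels, 3/22/60/13/2 | 429 | 31 / 49 | 49 / 71 | 67 / 85 |
| NYHA I–IV at visit, 10/45/40/5 | 429 | 37 / 51 | 57 / 74 | 75 / 88 |
| Improved/same/worse | 386 | 36 / 45 | 55 / 66 | 72 / 82 |
| Five change levels | 386 | 28 / 45 | 45 / 67 | 62 / 83 |
| NYHA I–IV at visit | 386 | 34 / 48 | 53 / 70 | 70 / 84 |

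The gap is about 8 to 22 points at 429 per arm and 9 to 22 at 386. It is smallest, about 10 points, for the three-level coding.

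**4. What the Wilcoxon reading would cost.** From ignoring order, nothing: it is the comparator above. Baseline class and stratum would still not be used as covariates.

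**5. Exercise capacity.** It is listed for comparison in 11.2.3. It is not in the endpoint list (3.1.2), the detailed visit schedule (8.4) or the visit table (8.8), where NYHA class is the functional assessment. Six-minute-walk papers remain in the reference list, but no such test is scheduled.

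**The case against.** The strongest reply is that the plan never says that NYHA change will be tested by chi-square. A reader might infer that it is assigned to that test, but 11.2.3 does not name NYHA, and 3.1.2 words the endpoint as a change in ranking, which can be taken as a numeric difference. The Wilcoxon test then applies and the power loss in the table disappears. This stands: the loss is conditional on the categorical reading.

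Two further inferences are tempting and unsupported. One is that the plan ignores baseline. The endpoint is a change, so baseline enters by subtraction; what is absent is a stated adjustment for entry class. The other is that the result would carry no direction or effect size. The proportions by arm would show direction, and a change score or an improved/not-improved indicator would fit the generalized linear model sentence and give a signed estimate.

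The power figures also favour the rank test, because a proportional shift is the alternative that suits it. The four-class case models class at the visit and not change. The 386 per arm allows for 10% loss but not separately for deaths before the visit, in a trial that plans on a 40% one-year control rate for a composite including death.

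Finally, the stakes are limited. Secondary analyses are exploratory, no decision rule rests on NYHA class, and the KCCQ also covers physical function (section 8.6). The exercise-capacity entry looks like leftover text; it is a separate correction and adds no weight to the NYHA point.

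What remains is that ordinal data are missing from every method in the section, no covariate is named, and two tests with different power are both open.

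**Conclusion.** The point holds as a gap in specification. Section 11.2.3 gives no method that both respects the order of NYHA class and adjusts for baseline class. If its categorical rule is applied, power falls by roughly 8 to 22 points, and by about 10 for improved/same/worse coding. These sizes rest on assumed distributions, a proportional shift with odds ratios of 1.3 to 1.5, and 386 to 429 patients per arm. If change is scored and tested by Wilcoxon, nothing is lost from ignoring order, but baseline class and stratum remain unused as covariates. Exercise capacity is listed for analysis and cannot be analysed, because it is not measured. The primary analysis and its conclusion are not affected.

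**What to change.** In section 11.2.3:

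- replace exercise capacity with NYHA functional class;
- analyse NYHA class at 6 and at 12 months with a proportional-odds model containing treatment, baseline NYHA class and the randomisation stratum, and report the common odds ratio with its confidence interval;
- name a stratified rank test as the fallback if proportional odds fails;
- state how deaths before the visit are handled, for example as a category ranked below class IV, or by analysing survivors with deaths shown alongside.

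Align the endpoint wording in 3.1.2 and the synopsis, so that the endpoint (class at the visit, given baseline class) and its analysis agree.

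The cost is wording and a check of the proportional-odds assumption. Baseline class, follow-up class and stratum are already collected, so no new data or patients are needed.

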5.3.2. Discontinuation Criteria Related to the Patient

The patients will be advised in the informed consent form that they have the right to withdraw from the study at any time without prejudice. In the event that a patient drops out of the study, a study stop form will be completed. In the study stop form, the investigator will record the date and the reason of the individual study termination. The patient will be informed that, in addition to their withdrawal, they can request that none of their data should be analyzed. Otherwise, their data remains in the intention-to-treat group.

Reasonable effort will be made to contact any patient lost to follow up during the course of the study, unless they have withdrawn consent and request that no additional contact be made, in order to complete assessments and retrieve any outstanding data and study supplies.

Once randomized, the patient stays within their group regardless of changes in NOXT treatment, and will be followed to the end of the study. An exception is women who become pregnant during the study, who will be discontinued from the study once pregnancy is identified.

Follow-up will also be stopped (data censored) in patients who reach the endpoints of cardiac transplantation or LVAD implantation. Those patients in whom protocol deviation or violation is noticed will remain in the intention-to-treat group and will be followed according to protocol. If a patient from the control group gets NOXT, they will also remain in the study and will be followed according to protocol.

Patients other than those who experience pregnancy, cardiac transplantation or LVAD implants will be followed according to the study protocol, regardless of whether they experience a primary endpoint. This will allow for recurrent event analyses.

Study therapy may be stopped in several circumstances: a) by participant request; b) if the participant's clinical situation changes and his provider prescribes oxygen therapy indefinitely or other therapy that precludes use of oxygen; or c) the participants become pregnant, undergoes cardiac transplantation or LVAD implant. All attempts will be made to continue outcomes assessments on these patients.

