11.2. Statistical Analysis Approaches

Primary analyses will follow the “intention-to-treat” principle; that is, individuals will be analyzed according to their assigned treatment group, whether or not they receive the study treatment as assigned. Every effort will be made to obtain follow-up data on all randomized subjects, whether or not they follow their assigned treatment. Preliminary Analyses

Our approach will involve close collaboration between clinical experts (on the Steering Committee and Scientific Advisory Committee) and biostatisticians, while ensuring appropriate blinding. Interim analyses of baseline variables (aggregated across intervention groups) will be conducted early in the study to ensure that the collected and derived data follow the assumed distributions, and that appropriate methods for identifying outliers and for computing clinical scores are implemented. Reports will provide a full description of the distributions of each study variable, along with indices of associated data quality, and include graphical displays. The amount and patterns of missing data, if any, will be characterized. Measures that are not normally distributed may be transformed to meet model assumptions. Before conducting final analyses, descriptive statistics will be generated using the total data set, ensuring that outliers or potential discrepancies in the data are resolved.

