11.2.2. Statistical Approaches to Testing for Treatment Differences

The primary analysis is in the intention-to-treat population that consists of all patients randomized. The primary study endpoint is the time to first event (all-cause death, HF-related hospitalization, life-saving CV procedure), as assessed by the CEC. The primary analysis will

use a Cox proportional hazard model relating the primary outcome and treatment indicator, adjusting for the stratification factor.

The null hypothesis (H0) is: The distribution of time to first event in the intervention group is identical to that in the control group. The alternative hypothesis (H1) is:

The distribution of time to first event in the intervention group differs from time to first event in the control group.

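### Secondary change scores have an unadjusted Wilcoxon test and a model with unnamed covariates; neither method nor visit is named as main (minor, primary result unaffected)

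*Combined protocol and SAP*

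**What the plan says.** Section 3.1.2 words the KCCQ, EQ-5D, PHQ-8 and PROMIS endpoints as changes and states: "Quality of life, symptom, and functional status endpoints will be measured at baseline and at 6 and 12 months follow up". It does not say which follow-up visit is the main one.

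Section 11.2.3 chooses methods by type of scale. For continuous measures: "Continuous endpoints will be compared using Wilcoxon rank-sum tests". The next sentence adds a second method: "Generalized linear models will be fit to assess the treatment effect on various endpoints adjusting for covariates for continuous, dichotomous or count data". The covariates are not listed and the two methods are not ranked. The same section sets the status of these results: "Secondary analyses are considered exploratory and will be tested at significance level of 0.05 without adjusting for multiple comparison".

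Section 11.2.2 specifies the primary Cox model as "adjusting for the stratification factor". Section 11.2.3 carries that approach over to time-to-event secondary endpoints, but does not mention the stratum for continuous ones.

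Section 11.2 allows that "Measures that are not normally distributed may be transformed to meet model assumptions".

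Section 11.3 gives 858 patients 80% power for a 0.2 SD difference in means by a two-sample t-test, a test that 11.2.3 does not plan. It does not say which visit is meant, or whether the SD is that of the score or of its change.

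**The concern.** Two things are at stake.

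The first is precision. A rank test on change uses baseline only by subtraction. When follow-up is imperfectly correlated with baseline, subtraction over-corrects, and a model with baseline as a covariate usually estimates the effect more precisely from the same data. The randomisation stratum is also left out, although the primary analysis uses it.

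The second is choice after the fact. Two unranked methods at two visits give up to four p-values per score, each read at 0.05. Which one becomes the reported result is not fixed in the supplied text. An exploratory label removes the claim to control error across endpoints. It does not settle which number is the result for one endpoint.

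**Working it through.** **Inputs from the documents.** 858 patients, 429 per arm; two-sided 5%; difference 0.2 SD; stated power 80%; drop-out 10% (all section 11.3). With 10% missing, 0.9 × 429 ≈ 386 per arm.

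**Assumption.** The baseline to follow-up correlation r is not in the documents. I take 0.5–0.7, with equal variances at the two times.

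**The plan's own figure.** Power = Φ(0.2·√(n/2) − 1.96).
- n = 386: 0.2 × 13.89 − 1.96 = 0.818, power 79.3%.
- n = 429: 0.2 × 14.65 − 1.96 = 0.969, power 83.4%.

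The stated 80% therefore agrees with the 10% drop-out given in the same section.

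**Wilcoxon on change, normal scores.** Efficiency relative to the t-test is 3/π = 0.955, so n becomes 386 × 0.955 = 368.6. Then 0.2 × √184.3 − 1.96 = 0.755, power 77.5%.

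**Baseline-adjusted model.** With unit score variance, change has variance 2(1 − r) and the adjusted outcome 1 − r². The ratio is (1 + r)/2. Power = Φ(0.2·√(386/(1 + r)) − 1.96), with 0.2 SD taken as the SD of change.

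| r | variance ratio | power |
|---|---|---|
| 0.5 | 0.75 | 89.4% |
| 0.6 | 0.80 | 87.4% |
| 0.7 | 0.85 | 85.4% |

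Over a wider range, r = 0.3 gives 93.1% and r = 0.9 gives 81.3%.

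**If 0.2 SD means the SD of the score.** Wilcoxon on change against the adjusted model gives 77.5% v 89.4% at r = 0.5, 85.9% v 93.5% at 0.6 and 93.9% v 97.3% at 0.7. The direction is the same and the gap narrows.

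**Shape of the scores.** Simulation with 386 per arm, r = 0.5–0.7, effect 0.2 SD of change on the underlying normal scale. Ranges cover repeated runs of 2,000 to 6,000 replicates.

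| Score | Wilcoxon on change | ANCOVA |
|---|---|---|
| Normal | 76–79% | 85–89% |
| 0–100 with ceiling (underlying mean 65, SD 25) | 74–75% | 83–88% |
| Lognormal, log-SD 0.6, untransformed | 74–77% | 74–82% |
| Lognormal, log-SD 1.0, untransformed | 71–75% | 54–67% |

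At log-SD 0.6 the two are about equal when r = 0.7; at log-SD 1.0 the ranking reverses. After a log transformation the lognormal score is the normal case again, so ANCOVA returns to about 85–89%. Type I error, checked for the first three shapes, was 4.2–5.2% for both methods.

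**Open choice of method and visit.** Simulated under no effect (386 per arm, 4,000 trials), the chance that at least one of four analyses of one score gives p < 0.05 is 11.8% (r = 0.7, between-visit correlation 0.8) to 14.0% (r = 0.5, between-visit correlation 0.7). For the two methods at one visit it is 6.6–8.0%.

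**The case against.** The strongest reply is that covariate adjustment is already planned. The generalized linear models may contain baseline and stratum, and if such a model is the main analysis nothing is gained. That stands as a limit: the efficiency figures apply only if the Wilcoxon test is what gets reported. What remains is a missing covariate list, ranking and visit.

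Second, the Wilcoxon test is valid and robust. Under strong skew it can have more power, and with heavy-tailed residuals (t with 3 degrees of freedom) it gave 90–93% against 86–89% for ANCOVA. This also stands. It is why transformation has to be settled beforehand and why the rank test should stay as a sensitivity analysis.

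Third, 11.2.3 does not name the questionnaires beside the Wilcoxon test. The link is inferred from scale type. Section 8.6 gives PHQ-8 in severity categories and EQ-5D as a profile plus a visual scale, so some forms could fall under the categorical tests. Section 11.2.4 refers to a Statistical Analysis Plan, for effect modifiers only, so the point is confined to the supplied text.

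A reader might infer two stronger points that the documents do not support:

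- *That the 80% in 11.3 is wrong or ignores missing scores.* It reproduces at 79.3% with the drop-out stated in that section.
- *That the 12-month scores are underpowered because late recruits never reach that visit.* This depends on which end-of-follow-up statement applies. Sections 4.3 and 11.3 end at the last patient's 6 months, 11.1 continues calls to the last 12-month visit, and 8.3 gives a calendar date. That conflict is a separate matter and adds no weight here.

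**Conclusion.** The concern holds as a minor improvement. In the supplied text, continuous secondary scores have an unadjusted test and an incompletely specified model, with no main method and no main visit. Making a baseline- and stratum-adjusted model the main analysis would raise power for 0.2 SD of change by about 8 to 12 percentage points (77.5% to 85.4–89.4%) for roughly normal scores, and by a similar amount under a ceiling.

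This rests on an assumed r of 0.5–0.7, equal variances, 10% missing, and the Wilcoxon test otherwise being the reported result. The gain is nil if the planned model already includes baseline and is the main one, and it can reverse under strong skew without transformation. Neither method is biased or invalid, the analyses are declared exploratory, and the primary result is unaffected.

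**What to change.** In section 11.2.3, before unblinding:

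1. Make one ANCOVA at 6 months the main analysis of each continuous score, with baseline score and the high-risk stratum as covariates. Six months is preferred because no patient is excluded from it by the end-of-follow-up rules in 4.3, 11.1 or 11.3.
2. Name in advance any score to be transformed for skewness, and the transformation, so that the permission in 11.2 does not become a choice made on unblinded data.
3. Keep the Wilcoxon test on change as a sensitivity analysis and report 12 months as supportive.
4. List which forms of PHQ-8 and EQ-5D are treated as continuous.
5. State how patients without a 6-month score enter the analysis, including deaths and those covered by "Follow-up will also be stopped (data censored) in patients who reach the endpoints of cardiac transplantation or LVAD implantation".

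In section 11.3, name the planned test and visit for the continuous endpoints and say which SD the 0.2 refers to. The 80% need not be withdrawn.

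The cost is SAP wording and one model per score. No new data, no change in sample size and no change to the primary analysis are needed.
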